#### 7.2.1 Liver Chemistry Stopping Criteria

Liver chemistry stopping criteria schematized in [Figure 1](#) are designed to ensure subject safety and to evaluate liver event etiology. Suggested actions and follow-up assessments are provided in [Section 12.2](#). A significant change in liver chemistry that does not satisfy stopping criteria may still be considered an AESI (see [Section 8.2.8](#)).

**Figure 1. Liver Chemistry Stopping Criteria and Increased Monitoring Algorithm**

## 7.2.2 QT Stopping Criteria

Study drug will be discontinued for a subject if either of the following criteria is met:

- QTcF >500 msec OR uncorrected QT >600 msec
- Change from screening or baseline in QTcF of >60 msec

One repeat ECG should be performed to confirm the accuracy and persistence of an initial result that fulfills the QT stopping criteria.

## 7.2.3 Suicidality Stopping Criteria

SPR001 is considered to be a central nervous system (CNS)-active study drug. Some CNS-active drugs may be associated with an increased risk of suicidal ideation in certain populations. Although SPR001 has not been shown to be associated with an increased risk of suicidal thinking or behavior when given to healthy volunteers, subjects will be monitored for such events during this study using the C-SSRS (see [Section 8.1.6.1](#)).

Individuals who provide a positive answer to question 3, 4, or 5 of the C-SSRS (on suicidal ideation) at screening or baseline are not eligible for this study. The Investigator should immediately contact the Medical Monitor to discuss possible study drug discontinuation and appropriate safety follow-up for a subject who provides a positive answer to question 3, 4, or 5 of the C-SSRS at any visit after baseline. This will also be considered an AESI (see [Section 8.2.8](#)).

The subject's HADS score should also be evaluated in conjunction with the C-SSRS (see depression stopping criteria in [Section 7.2.5](#)).

#### **7.2.4 Adrenal Insufficiency Stopping Criteria**

If a subject dosed with study drug exhibits clinically significant signs of acute adrenal insufficiency, such as postural hypotension, nausea, and abdominal pain, the Investigator should consider withholding the subject's dose(s) of SPR001, initiate appropriate corticosteroid therapy, and contact the Medical Monitor. If there is no clear explanation for the subject's acute adrenal insufficiency, such as inadequate corticosteroid replacement dosing or low circulating levels of plasma cortisol, the Investigator should review the subject with the Medical Monitor for possible study drug discontinuation.

#### **7.2.5 Depression Stopping Criteria**

Individuals who score >12 on either the depression or anxiety subscale of the HADS (see [Section 8.1.6.2](#)) at screening or baseline are generally not eligible for this study. The Investigator should immediately contact the Medical Monitor to discuss possible study drug discontinuation and appropriate safety follow-up for a subject who scores >12 on either the depression or anxiety subscale of the HADS at any visit after baseline. This will also be considered an AESI (see [Section 8.2.8](#)). Reasons for an elevated HADS score (aside from clinical depression) include chronic pain and stress.

#### **7.2.6 Reproductive Hormone Stopping Criteria**

Subjects with CAH can be expected to have abnormal reproductive hormone levels because deficient 21-hydroxylase enzyme activity leads 1) to elevated levels of cortisol precursors that are shunted into reproductive hormone biosynthetic pathways and 2) to low levels of the cortisol that normally provides negative feedback on the HPA axis. Standard-of-care therapy with glucocorticoid and mineralocorticoid replacement typically does not fully normalize adrenal steroid production pathways and signaling systems, including ACTH and CRF levels. Thus, subjects with CAH can be expected to have abnormal plasma concentrations of various androgens and progestogens at baseline. Therapy with an effective CRF receptor antagonist may in fact shift the balance between various intermediates in the steroid biosynthetic pathway.

If a subject experiences changes from baseline in reproductive hormone(s), the Investigator should contact the Medical Monitor to discuss whether such changes represent clinically significant reproductive abnormalities, potential risks to the subject, possible study drug discontinuation, and appropriate safety follow-up. These changes include but are not limited to significant changes in LH, FSH, inhibin B, SHBG, estradiol, prolactin, or progesterone; testicular dysfunction in men; and changes in menstrual cyclicity in women.

#### **7.2.7 Potentially Clinically Significant Adverse Events**

Clinically significant AEs include but are not limited to SAEs ([Section 8.2.2](#)), AEs leading to study drug discontinuation/study withdrawal, DLTs ([Section 7.1](#)), and AESIs ([Section 8.2.8](#)) that are each considered at least possibly related to study drug. The occurrence of any clinically

significant AE will receive special consideration in decisions regarding continuation or suspension of dosing or enrollment and will be reported to the SRC within 1 day of awareness for immediate review.

Section 12.3 also provides a list of signs and symptoms (Section 12.3.1) and a list of laboratory findings (Section 12.3.2) that constitute potentially clinically significant AEs not otherwise specified among the foregoing individual treatment stopping criteria. These provide guidelines for a level of moderate-severe abnormality in safety findings that could cause harm to subject health and may preclude further study drug dosing. These lists are intended to guide the Investigator and are not meant to be a set of absolute criteria. Safety parameters not included in the list may be interpreted in a similar fashion according to Investigator judgment. Common Terminology Criteria for Adverse Events (CTCAE) severity grading should also be referenced (Section 8.2.3.1).

### 7.3 Participant Withdrawal from the Study

Subjects may voluntarily withdraw from the study or be withdrawn by the Investigator at any time. If a subject withdraws from the study, the Investigator must document the date and primary reason for the withdrawal on the appropriate eCRF.

Reasons for a subject to discontinue study drug or to withdraw from this clinical study include but are not limited to the following:

- Withdrawal of informed consent
- Fulfilling individual treatment stopping criteria (see Section 7.2).
- AE(s)
- Protocol deviation or noncompliance with study procedures/restrictions
- Desire or need to start a contraindicated therapy or another therapy for CAH
- Study termination by the Sponsor
- Lost to follow-up

### 7.4 Lost to Follow-up

A subject will be considered lost to follow-up if the subject repeatedly fails to attend scheduled visits and study personnel are unable to contact the subject.

The following actions must be taken if a subject fails to attend a required study visit:

- The site must attempt to contact the subject and reschedule the missed visit as soon as possible, counsel the subject on the importance of maintaining the assigned visit schedule, and ascertain whether the subject wishes to and/or should continue in the study.
- Before a subject is deemed lost to follow-up, the Investigator or designee must make every effort to regain contact with the subject, including, where possible, making 3 telephone calls to the subject and, if necessary, sending a certified letter to the

subject's last known mailing address (or local equivalent methods). Attempts to contact the subject should be documented in the subject's medical record.

- If the subject continues to be unreachable, the subject will be considered to have withdrawn from the study with a primary reason of lost to follow-up.

## 8 STUDY ASSESSMENTS AND PROCEDURES

This section describes what study assessments and procedures will be performed and how they will be conducted. The timing of study assessments and procedures is provided in the Schedule of Activities in [Section 1.3](#).

### 8.1 Safety Assessments

Safety assessments will consist of monitoring and recording all AEs (including SAEs, AEs leading to discontinuation/withdrawal, DLTs, and AESIs), physical examination, vital signs assessment, ECGs, clinical laboratory, and monitoring for suicide risk and depression/anxiety. AE procedures are described in [Section 8.2](#).

#### 8.1.1 Physical Examination

A full physical examination should include assessments of the cardiovascular, respiratory, gastrointestinal, neurological, and musculoskeletal systems; head, eyes, ears, neck, and throat (HEENT); thyroid, skin, and extremities. The full physical examination may exclude rectal, genitourinary, and breast exams.

An abbreviated physical examination should include the following components: cardiovascular, respiratory, abdomen, musculoskeletal, HEENT, and skin.

As part of both the full and abbreviated physical examinations, female subjects will be asked about the date, duration, and nature of their last menstrual period.

As part of the examination of the skin where specified in the Schedule of Activities, acne will be evaluated in all subjects and hirsutism will be evaluated in female subjects. Acne severity will be graded using an Investigator's Global Assessment (IGA) score per [FDA guidance](#). Hirsutism will be graded using a modified Ferriman Gallwey (mFG) score ([Yildiz et al, 2010](#); [Martin et al, 2018](#)). The mFG scores each of 9 body areas on a scale of 0 (no hair) to 4 (hairiness typical of a man), with the sum of the separate scores providing a hormonal hirsutism score.

Investigators should pay special attention to clinical signs related to previous serious illnesses.

#### 8.1.2 Vital Signs

Vital signs consist of systolic and diastolic blood pressure, pulse rate, respiration rate, and body temperature. Vital signs will be measured as specified in the Schedule of Activities and as clinically indicated.

#### 8.1.3 Body Weight, Height, and BMI

Body weight will be measured at every visit using a calibrated balance. The balance should be placed on a hard flat surface and checked for zero balance before each measurement. The subject should stand unassisted, in the center of the platform, and be asked to look straight ahead, standing relaxed but still.

Height needs to be recorded at Visit 1 only.

BMI will be calculated for every visit using height and weight measurements.

#### **8.1.4    Electrocardiogram**

A 12-lead ECG will be obtained using an ECG machine that automatically calculates the heart rate, QRS, QT, and QTc intervals, preferably using Fridericia's formula. Any ECG measurement assessed by the Investigator as a clinically significant abnormality should be recorded in the AE section of the eCRF and monitored until resolution.

Refer to [Section 7.2.2](#) for QT individual treatment stopping criteria and any additional ECGs that may be necessary.

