#### 5.1.2 Exclusion Criteria for Subjects Who Completed Study SPR001-201

Subjects who completed Study SPR001-201 will not be eligible for this study if they meet any of the following criteria:

1. Experienced a clinically significant AE (defined in [Section 7.2.7](#)) considered at least possibly related to SPR001 in Study SPR001-201
2. If screening for this study occurs >3 months after the subject's final follow-up visit in Study SPR001-201, the subject will be screened for any clinically significant unstable medical condition, medically significant illness, or chronic disease occurring within 30 days of screening, including but not limited to the following:

- a. A malignancy or <3 years of remission history from any malignancy, other than successfully treated localized skin cancer
- b. Presence of clinically significant renal disease, as evidenced by an eGFR of <60 mL/min/1.73 m^2
- c. Current or chronic history of liver disease, or known hepatic or biliary abnormalities (with the exception of Gilbert's syndrome or asymptomatic gallstones)
- d. Confirmed positive test at screening for active hepatitis B, hepatitis C, or HIV

3. If screening for this study occurs >3 months after the subject's final follow-up visit in Study SPR001-201, the subject will be screened for clinically significant psychiatric disorders by history and from the M.I.N.I. conducted at screening. The subject will be excluded if screening reveals evidence of current major depressive episode, bipolar disorder, schizophrenia, schizoaffective disorder, major depressive disorder with psychotic features, or any other psychotic disorder within the preceding 6 months.

4. Is at increased risk of suicide on the basis of the Investigator's judgment or the results of the C-SSRS conducted at screening and baseline (e.g., C-SSRS Type 3, 4, or 5 ideation during the preceding 6 months or any suicidal behavior within the past 12 months)

5. Has a HADS score >12 for either depression or anxiety at screening or baseline

6. Clinically significant abnormal clinical or laboratory assessments must be discussed with the Medical Monitor to determine eligibility for this study. Abnormal assessments that must be reviewed to determine eligibility include but are not limited to:

- a. Clinically meaningful abnormal ECG results, in the opinion of the Investigator
- b. QTcF >450 msec for male participants or >470 msec for female participants
- c. ALT >2x ULN

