8.6. ECGs

A summary of ECG parameters, parameters reported separately QTcF, PR interval, QT interval, QRS duration, RR, and HR, will be summarized in terms of observed values and change from baseline.

Subjects without post-baseline measurement for a given treatment period will be excluded from the summary statistic (e.g., denominator of the summary statistic) for that time point.

All recorded values by central reader at ECG core lab for the standard 12-lead electrocardiogram parameters will be presented in a by-subject listing.

Outlier Analysis

The number of subjects with absolute ECG values and change from baseline in the ranges shown in [Table 6](#) will be presented in Electrocardiogram Outlier Summary by Visit and Time Point.

In addition in the same summary, QTcF will also be summarized by the following categories, Normal (males <430, females ≤450), Borderline (males (>430, ≤450); females (>450, ≤470)) and Prolonged (males >450, females >470).

Individual ECG data collected during the study will be presented in a listing. A separate listing of subjects with values of QTcF > 500 msec or an increase > 60 msec will be provided, as necessary.

Figures

Cumulative distribution plots will be provided for maximum change in QTcF at Week 12.

Investigator Assessment of ECG Readings

The investigators' assessment of ECGs as normal, abnormal and clinically significant, or abnormal but not clinically significant will be summarized for baseline and for each visit.

Table 6: ECG Outlier Thresholds

Heart Rate (bpm)	Heart Rate Change from Baseline (bpm)	PR Interval (msec)	PR Percentage Change from Baseline (%)	QRS Interval (msec)	QTcF (msec)	QTcF change from Baseline (msec)
>120	>20	> 200	> 15	> 120	Males:	≤ 30
>130	>30	> 220	> 25			≥ 430, ≤ 60
						> 60
						> 430
						> 450
						> 470
						> 480
						> 500
					Females:	
						≤ 450
						> 450
						> 470
						> 480
						> 500

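### Protocol 8.1.4 only prefers Fridericia's correction, although the QTc entry-review limits, stopping limits and SAP summaries are all on QTcF, and neither document says how QTcF is derived.

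*Protocol*

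**What the plan says.** **Measurement.** Protocol 8.1.4 calls for a 12-lead ECG from a machine that "automatically calculates the heart rate, QRS, QT, and QTc intervals, preferably using" Fridericia's formula. It names no fallback formula and does not ask for recalculation.

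**Entry review.** Protocol 5.1.2 and 5.2.3 list "QTcF >450 msec for male participants or >470 msec for female participants". This is a trigger for discussion with the Medical Monitor and not an automatic exclusion; the lead-in is "Abnormal assessments that must be reviewed to determine eligibility include but are not limited to".

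**Stopping.** Protocol 7.2.2 uses QTcF above 500 msec or uncorrected QT above 600 msec, and separately "Change from screening or baseline in QTcF of >60 msec". One repeat ECG is to confirm a qualifying result.

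**Analysis.** SAP 8.6 summarises QTcF, PR, QT, QRS, RR and heart rate. On the source it says: "All recorded values by central reader at ECG core lab for the standard 12-lead electrocardiogram parameters will be presented in a by-subject listing". It sorts QTcF as "Normal (males <430, females ≤450), Borderline (males (>430, ≤450" msec for men, with male values above 450 called prolonged. It plans a separate listing for QTcF above 500 msec or an increase above 60 msec, and adds: "Cumulative distribution plots will be provided for maximum change in QTcF at Week 12". SAP Table 2 sets the ECG baseline at Day 1 before dosing. The derivations in SAP 6.6 contain no QTcF formula.

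**The concern.** The measurement section permits a quantity that the decision and analysis sections do not use. If a machine prints a QTc under another correction and the site reads it against a QTcF limit, a change in heart rate can look like prolongation, and real prolongation can be hidden at a low rate. The repeat ECG in 7.2.2 would not reveal this, because the same machine would apply the same formula again.

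Change in ECG is among the primary safety endpoints (Protocol Section 3). The protocol plans about 8 sites and SAP 4.3 gives a final sample of 11, so a few discordant values could show in the tables if they reached the analysis.

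The two documents also differ on where ECG values come from. The protocol names a central laboratory for clinical chemistry (8.1.5) and a central radiologist for scrotal ultrasound (8.5.4.1). For ECGs it mentions only the machine and the Investigator. The SAP assumes a central reader.

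**Working it through.** The documents state no figure for a difference between formulas, so there is none to reproduce. The alternative formula, the true QTcF and the heart rates below are all assumptions.

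**Formulas**, with RR = 60/HR in seconds:
- Fridericia: QTcF = QT / RR^(1/3), so QT = QTcF × RR^(1/3)
- Bazett: QTcB = QT / RR^(1/2) = QTcF × (HR/60)^(1/6)
- Framingham: QT + 154 × (1 − RR)
- Hodges: QT + 1.75 × (HR − 60)

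**Example**, QTcF 400 msec at 100 bpm: RR = 0.6 and QT = 400 × 0.6^(1/3) = 337.4. Bazett is 400 × (100/60)^(1/6) = 435.5. Framingham is 337.4 + 61.6 = 399.0. Hodges is 337.4 + 70 = 407.4.

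**Difference from true QTcF (msec)**

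| HR (bpm) | Bazett, QTcF 400 | Bazett, QTcF 410 | Framingham, QTcF 400 | Hodges, QTcF 400 |
|---|---|---|---|---|
| 50 | −12.0 | −12.3 | −5.7 | +7.6 |
| 60 | 0 | 0 | 0 | 0 |
| 80 | +19.6 | +20.1 | +1.9 | −1.6 |
| 90 | +28.0 | +28.7 | +0.8 | +1.9 |
| 100 | +35.5 | +36.4 | −1.0 | +7.4 |

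At 110 bpm and QTcF 400, Bazett differs by +42.5 and Hodges by +14.3.

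**Effect on the limits if the value is Bazett**
- 450 msec line, men: crossed when HR exceeds 60 × (450/QTcF)^6. That is 78.8 bpm for a true QTcF of 430 and 90.8 bpm for 420.
- Low rate: at 50 bpm the factor is (50/60)^(1/6) = 0.970, so a man with a true QTcF of 460 reads 460 × 0.970 = 446 and is not flagged.
- 500 msec line: crossed at a true QTcF of 476.6 at 80 bpm or 459.2 at 100 bpm.
- Change above 60 msec: with QTcF constant at 400, a move from 60 to 100 bpm gives +35.5 and from 50 to 100 bpm gives +47.5. From 60 bpm, a change of 60 msec needs 60 × (460/400)^6 = 138.8 bpm.

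**The three SAP wordings**
- Male Normal is below 430 and Borderline is above 430, so exactly 430 has no category. The female bands meet at 450 without a gap.
- The stopping rule takes change from screening or baseline. The SAP listing gives no reference point, and the SAP ECG baseline is Day 1. If the listing follows that baseline, a subject stopped for a change from screening could be missing from it.
- Protocol 1.3 schedules on-treatment ECGs at Weeks 4, 8 and 12. A maximum at one visit is either just that visit's change or a maximum over visits with the wrong label.

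**The case against.** The abbreviation QTcF fixes the formula in each limit, so reading a Bazett value against it would depart from the protocol. The machine must also output QT and heart rate, so QTcF can be had whatever its default. Both points stand. What is missing is an instruction to convert, or any check that would catch a failure to do so.

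Several stronger readings are tempting and are not supported:
- *Every ECG limit is a QTcF limit.* No. Stopping also uses uncorrected QT above 600 msec, and SAP Table 6 has heart-rate, PR and QRS thresholds. Only the QTc limits are affected.
- *QTc will be wrong by 20 to 36 msec.* This holds only for Bazett, with QTcF near 400 to 410 and 80 to 100 bpm. The documents give none of these.
- *Heart rate alone could stop treatment under the change rule.* Not within 60 to 100 bpm, as shown above.
- *The SAP tables contain mixed formulas.* Not shown. The SAP cites a core lab and reports QT and RR. The protocol's silence on a core lab does not prove that none was used.
- *The >60 msec listing uses baseline only, and the Week 4 and Week 8 peaks are dropped.* The listing gives no reference, and the plot wording is ambiguous. SAP 8.6 lists all individual ECGs and plans an outlier summary by visit. The figure index in SAP 11.3 contains no ECG plot.

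**Conclusion.** The inconsistency is real and minor. Protocol 8.1.4 leaves the correction open while the QTc entry-review limits, stopping limits and SAP summaries depend on one formula. No derivation closes the gap, and the two documents do not agree on the source of the readings.

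The size is conditional. Under the Bazett assumption at a true QTcF of about 400 to 410, readings would be about 12 msec low at 50 bpm, 20 msec high at 80 bpm and 36 msec high at 100 bpm. Under Framingham or Hodges they would be within 10 msec at 80 to 100 bpm. If all machines used Fridericia, or a core lab recalculated QTcF, the difference in the analysed values is zero. How many sites used another formula cannot be known from the documents.

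The male value of exactly 430 is a definite gap as written, though it affects one value. The listing reference and the plotted maximum need clarification; neither is a demonstrated loss of data.

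**What to change.** - **Protocol 8.1.4:** reconcile with the QTcF limits in 5.1.2, 5.2.3 and 7.2.2 by requiring Fridericia, or by computing QTcF = QT/RR^(1/3) from the recorded QT and RR (or heart rate) before a limit is applied. No limit changes.
- **SAP 8.6:** derive QTcF the same way for every ECG. State whether a core lab supplied the values, and bring the SAP and protocol into agreement on this.
- **SAP 8.6, categories:** define male Normal as ≤430 msec.
- **SAP 8.6, listing:** state the reference for the increase above 60 msec so that it agrees with the screening-or-baseline wording of Protocol 7.2.2.
- **SAP 8.6, plot:** define the plotted value as the maximum change over all on-treatment ECGs, or call it the Week 12 change.

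The cost is one protocol sentence and a few lines of SAP text and programming. QT and heart rate are already collected, so no new data are needed. Since SAP 4.3 already gives the final sample size, the protocol edit is unlikely to alter entry decisions in this study; the SAP derivation can still be applied to all 11 subjects.

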#### **8.1.5    Clinical Laboratory**

A list of study-required clinical laboratory tests is provided in [Section 12.4](#). A list of potentially clinically significant laboratory findings is provided in [Section 12.3.2](#).

All study-required clinical laboratory tests must be conducted in accordance with the laboratory manual and will be performed by a central laboratory.

The Investigator must review the laboratory report, document the review, and record any clinically significant laboratory findings that occur during the study in the AE section of the eCRF. Laboratory reports must be filed with the source documents. Clinically significant laboratory findings are those that are not associated with the underlying disease, unless judged by the Investigator to be more severe than expected for the subject's condition.

All laboratory tests with values considered clinically significantly during the treatment period or within 30 days after the last dose of study drug should be repeated at least weekly until the values return to normal or baseline or are no longer considered clinically significant by the Investigator or Medical Monitor. If such values do not return to normal/baseline within a period of time judged reasonable by the Investigator, the etiology should be identified and the Sponsor notified.

